# 8.5. Removal of Subjects from Therapy or Assessment

### 8.5.1 Screening failures

Subjects who signed the informed consent form and performed screening and/or baseline activities (either completely or partially) but were not randomized to the study are considered screening failures.

If the subject is found to be not eligible at this visit, the investigator should complete the eCRF.

The primary reason for screen failure should be recorded in the eCRF using the following categories:

- PTE/AE.
- Did not meet inclusion criteria or did meet exclusion criteria.
- Significant protocol deviation.
- Lost to follow-up.
- Voluntary withdrawal, <specify reason>.
- Study termination.
- Other, <specify reason>.

Subject numbers assigned to subjects who fail screening should not be reused.

# 8.5.2 Discontinuation or Withdrawal of Individual Subjects

If a randomized subject terminates the study prematurely for any reason, all attempts should be made by the investigator to perform the procedures for the early termination visit (same as for the week 6 visit) and determine the primary reason for the termination and where possible the primary underlining reason, providing as much as detail as possible, and documenting the information on the eCRF. Randomized subjects will not be replaced.

The primary reason for discontinuation or withdrawal of the subject from the study should be noted using the following categories:

- (1) Pretreatment event (PTE) or Adverse Event (AE). The subject has experienced an adverse event or pre-treatment event that requires early termination because continued participation imposes an unacceptable risk to the subject's health or the subject is unwilling to continue because of the adverse event or pre-treatment event.
- (2) Noncompliance with investigational medicinal product (IMP). This includes subjects who did not take the study drug for more than 6 consecutive days.
- (3) Major protocol deviation. The subject failed to meet protocol entry criteria or did not adhere to protocol requirements, and continued participation poses an unacceptable risk to the subject's health, or a major protocol deviation occurred at the site such as the blind was broken.
- (4) Withdrawal of consent. The subject (or subject's legally acceptable representative) wishes to withdraw from the study. The reason for withdrawal, if provided, should be recorded in the case report form (eCRF). Subjects may withdraw from the study at any

Amendment 04, Final Version 1.0
Protocol No.: BB-2001-201b
EudraCT No.: 2017-000877-35
Amendment 04, Final Version 1.0
07/Nov/2018
Page 65 / 142

time at their own request without giving reasons and without any disadvantageous consequences for their subsequent medical care.

- (5) Lost to follow-up. The subject did not return to the clinic and attempts to contact the subject were unsuccessful. Attempts to contact the subject must be documented.
- (6) Subject does not fulfil randomisation criteria.
- (7) Other.

In the case of study termination by the sponsor, institutional review board (IRB), independent ethics committee (IEC), or regulatory agency, reason for withdrawal should be captured as Other, Study Termination.

If the subject is found to be pregnant during the study, the subject must be withdrawn immediately. The reason for withdrawal should be "major protocol deviation" unless there was a complication of the pregnancy which led to withdrawal, in which case the reason for withdrawal should be "adverse event(s)". The procedure is described in Section 9.7.

### 8.6. Treatments

### **8.6.1** Treatments Administered

BenevolentAI Bio will supply the IMP consisting of:

- Bavisant 0.5 mg tablets
- Bavisant 1 mg tablets
- Bavisant 3 mg tablets
- Matching placebo tablets

### **8.6.2** Identity of Investigational Product(s)

# **Experimental treatment:**

Product Name: Bavisant tablets 0.5/1/3 mg

Drug substance: Bavisant dihydrochloride monohydrate

Pharmaceutical Form: Tablets containing Bavisant dihydrochloride monohydrate equivalent

to 0.5/1/3 mg of Bavisant

Administration route: Oral use

Dosage: Once daily administration

Manufacturer: Nuvisan GmbH, [name]

Control treatment:

Control substance: Placebo Pharmaceutical Form: Tablets

Amendment 04, Final Version 1.0
Protocol No.: BB-2001-201b
EudraCT No.: 2017-000877-35
Page 66 / 142

Administration route: Oral use

Dosage: Once daily administration

Manufacturer: Nuvisan GmbH, [name]

The IMP will be supplied in wallet cards. The IMP will be identifiable by a unique identification number. The wallet cards will contain a surplus of tablets to cover the treatment period and visit windows. The IMP should be stored at 25°C; excursions permitted to 15°C to 30°C.

Each card of investigational medication will be labelled with pertinent study information and country-specific regulatory caution statements in country-specific language(s).

### 8.6.3 Dosages and Regimen

Each subject who qualifies for the study will receive wallet cards containing tablets of double-blind study medication. Subjects will receive 1 wallet card of their assigned treatment at Visit 1 (for 2 weeks treatment period) and 2 wallet cards at Visit 2 (for 4 weeks treatment period).

Subjects will be instructed to take 1 tablet orally per day at the same time in the morning, with or without food. The first dose is to be taken the day after randomisation when study medication has been dispensed to the subject.

The investigator or designee must instruct the subject to bring each of their study medication containers (wallet cards) to each clinic visit, regardless of whether the study medication cards are empty.

# 8.6.4 Packaging and Labelling

IMP manufacture will be performed according to Good Manufacturing Practice (GMP) standards and according to the currently valid version of the respective national laws applicable at Nuvisan, Germany. Identity and stability of the substance for the duration of the study are ensured and documented through Certificates of Analyses.

Products' labelling will show at least the following information:

- Name and address and contact phone of Sponsor and CRO.
- Trial reference code and EudraCT Number.
- Pharmaceutical dosage form, route of administration and quantity of dosage units.
- The number of the IMP, batch number and expiry date.
- The statement "for clinical trial use only".
- The statement "keep out of the reach of children".
- The medication number and the Patient Number.
- Storage conditions.
- Name, principal investigator.

Amendment 04, Final Version 1.0 07/Nov/2018 Page 67 / 142

If applicable, local or country specific requirements regarding labelling of the blister wallets are also to be considered.

# 8.6.5 Storage and Disposition of Study Drug

At each study site, the investigator is responsible for the correct storage and handling of the IMP. The IMP must be stored in a place with access limited to the investigator and/or especially authorized personnel of the local study team only, i.e. study nurse or study coordinator.

The temperature of the storage area must be monitored and documented. The investigator is required to inform the responsible monitor immediately in cases of deviation of the storage temperature from the required range ( $+15^{\circ}$ C -  $+25^{\circ}$ C). Furthermore adherence to the storage conditions will be checked routinely by the monitor during the on-site visits.

# 8.6.6 Method of Assigning Subjects to Treatment Groups

A computer-generated randomisation scheme by region will be provided by Nuvisan according to Sponsor specification.

Subjects will be randomized in order to have 200 completed subjects. At the end of the baseline period on day -1, all subjects fulfilling the inclusion and exclusion criteria will be randomly allocated to one of the 4 treatment groups at a ratio of 1:1:1:1.

Treatment group 1: Bavisant 0.5 mg tablets
Treatment group 2: Bavisant 1.0 mg tablets
Treatment group 3: Bavisant 3.0 mg tablets

Treatment group 4: Placebo tablets

The randomisation will be stratified by region and by the polysomnography and the MWT assessment which will be performed to a subset of subjects (around 50%). The information on whether the subject will do the polysomnography and the MWT assessment will be collected first and the randomisation will be performed based on this information. A first block of medication according to the randomisation scheme created will be provided to each site. Upon completion of the first block of medication, the site should request a new supply of medication. In this case, if the subject will perform both the polysomnography and the MWT assessment, the randomisation number being provided will be selected as the first available from the bottom of the randomisation list; otherwise the subject will receive the maximum available subject number. With this method (also known as down-up / up-down) the randomisation can be stratified by polysomnography/MWT assessment with one single randomisation list and so guaranteeing a similar 1:1:1:1 distribution between strata.

The randomisation number will consist of a 3-digit number which will be linked to the respective electronic case report form (eCRF) number.

At the end of the baseline period, subjects will be randomly allocated to 1 of the 4 treatment groups and given the IMP with the next available randomisation number in either ascending or descending sequence. The 3-digit randomisation number is printed on the labels of the study medication and will uniquely identify the IMP which is assigned to the subject. Each subject must

Amendment 04, Final Version 1.0 07/Nov/2018 Page 68 / 142

be given only the IMP carrying his or her randomisation number. The investigator will document the randomisation number in the eCRF and IMP accountability records.

The randomisation schedule will link sequential medication numbers to treatment codes. The medication numbers will be blocked to facilitate attainment of a homogeneous distribution of treatment groups.

The randomisation schedule will be kept at Nuvisan's CTS department.

The investigator must keep a subject identification list including sufficient information to link records, i.e. eCRF, eDiary, and subject files/hospital records. Furthermore, a list of all subjects screened for the study should be kept in the ISF. The identity of the study subjects (subject number, year of birth, and age at screening), date of informed consent, and date of inclusion, or the reason for non-inclusion of the subjects at screening must be recorded in this subject screening/enrolment randomisation log.

## **8.6.7 Blinding**

Study treatments are blinded and the randomisation schedule and the allocation to treatment groups will not be known to the investigator, the sponsor, or any other person involved in the conduct of the study, except in case of an emergency if knowledge of the IMP is necessary to provide optimal treatment to the subject in an emergency situation.

For each subject, the investigator will receive an emergency envelope identified by the study code and the medication number, and containing information about the therapy regimen. In case of any subject-related event that requires unblinding (e.g. emergency), the investigator will be allowed to open the emergency envelope and find out the therapy regimen of the subject. If possible the sponsor or his responsible representative should be contacted prior to opening the envelope. Any unblinding must be documented with the date, time, and reason for unblinding and the sponsor or his responsible representative must be notified; the subject should be withdrawn from the study if medically indicated. However, such subjects may remain in the study "under observation" only.

To ensure the scientific integrity of the study, it is imperative that all emergency envelopes (open or sealed), as well as any documentation on unblinding of emergency envelope(s) be returned to the sponsor at the end of the study.

### 8.6.8 Treatment Adherence

The IMP will be self-administered by the subjects as once daily oral tablet in the morning. At visit 2 and visit 3, subjects will return any empty and non-used treatments providing information to study personnel regarding their compliance with study medication. Compliance will be monitored by study personnel at the site by using the source documents and will be recorded in the eCRF.

Every visit after baseline will be used for dispensing new medication and collecting used medication in order to closely promote the treatment adherence.

Amendment 04, Final Version 1.0 07/Nov/2018 Page 69 / 142

### 8.6.9 Overdose

An overdose is defined as a known deliberate or accidental administration of investigational drug, to or by a study subject, at a dose above that which is assigned to the individual subject according to the study protocol.

All cases of overdose (with or without associated AEs) will be documented on an Overdose page of the eCRF, in order to capture this important safety information consistently in the database. Cases of overdose without manifested signs or symptoms are not considered AEs. AEs associated with an overdose will be documented on AE eCRF(s).

SAEs associated with overdose should be reported according to the procedure outlined in Section 9.7.1.

In the event of drug overdose, the subject should be treated symptomatically.

# 8.6.10 Drug Accountability

The investigator or designee must document the receipt, dispensing, and return of IMP supplies and materials provided for this study in specific accountability forms included in the investigator's study file (ISF). The original form will be retrieved from the study site by the responsible monitor, and the investigator will retain a copy. Documentation of drug accountability for individual subjects will be captured in the eCRF.

The investigator or designee must ensure that the sponsor-supplied drug is used in accordance with the protocol and is dispensed only to subjects enrolled in the study. Upon receipt of sponsor-supplied drug, the investigator or designee must verify the contents of the shipments against the packing list. The verifier should ensure that the quantity is correct, and the medication is in good condition. If quantity and conditions are acceptable, they should acknowledge the receipt of the shipment (by signing the bottom half of the packing list and faxing per instructions provided on the form). If there are any discrepancies between the packing list and the actual product received, Linical must be contacted to resolve the issue. The packing list should be filed in the investigator's essential document file.

The investigator or designee must maintain 100% accountability for all sponsor-supplied drugs received and dispensed. Proper drug accountability includes, but is not limited to:

- Continuously monitoring expiration dates if expiry date is provided to the investigator or designee.
- Frequently verifying that actual inventory matches documented inventory.
- Verifying that the log is completed with the drug lot/medication ID/job number used to document each dose.
- Verifying that all containers used/assigned are documented accurately on the log.
- Verifying that required fields are completed accurately and legibly.

If any dispensing errors or discrepancies are discovered, the sponsor must be notified immediately.

Protocol No.: BB-2001-201b EudraCT No.: 2017-000877-35 Amendment 04, Final Version 1.0 07/Nov/2018 Page 70 / 142

Residual medication (complete blisters) must be returned to the sponsor, who will be responsible for accountability and destruction. If the site is responsible for destruction, the process must be done once the accountability is verified by the study monitor. The investigator is not permitted to dispense any study medication to persons not taking part in the study. Non-used drug will be returned to the centre at week 2 and week 6, and compliance will be assessed as:

Compliance (%) = 
$$\frac{\text{(Tablets dispensed)} - \text{(Tablets returned)}}{\text{Total number of days between visits}} \times 100$$

Amendment 04, Final Version 1.0
Protocol No.: BB-2001-201b
EudraCT No.: 2017-000877-35
Amendment 04, Final Version 1.0
07/Nov/2018
Page 71 / 142

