- (7) Pharmacogenomic blood sample to be obtained in subjects who specifically consented for this exploratory analysis.
- (8) The eye examination should be performed after the last treatment on Day 42 and before the follow up safety call.
- (9) Subjects will be instructed to have already taken their normally scheduled dose of anti-parkinsonian medication and their IMP prior to arriving at the study site in order to have their UPDRS Part III evaluated in ON (within approximately 1 to 3 hours after taking their levodopa dose). UPDRS in OFF will not be evaluated.
  - It is recommended that all assessment (s) establishing eligibility for the study to be performed first.
- (10) Any positive finding on the HAM-D, C-SSRS, or BPRS+ scales during the study will be referred to a trained mental health professional to be followed.
- (11) MWT and Polysomnography will be performed on a minimum of 50% of subjects (all recruited in sites with sleep units available)
- (12) Treatment will be taken from Day 1 to Day 42, both inclusive.

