6 ANALYSIS SETS

The safety population (SAF) will be defined as all subjects who have received at least one dose of the study treatment.

Sponsor BenevolentAI Bio

Project Code ... BB-2001-201b

The intent to treat population (ITT) will be defined as all randomized subjects who have taken at least one dose of study treatment.

The per protocol population (PP) will be defined as all subjects in the FAS who do not experience a major protocol deviation.

Protocol deviations will be defined as deviations from the procedure outlined in the protocol. Protocol deviations will be identified for each patient in the Data (blind) Review & Evaluability Determination meeting will be held prior to the treatment unblinding. They will be assessed as “minor” or “major” according to the possible impact expected on efficacy results. Minor and major protocol deviations will be fully documented in the Protocol Deviation Document prior to unblinding. Specific data sets will be produced and transferred to Biostatistics department in order to allow the appropriate definition for the Per Protocol Population.

Since the reasons for excluding patients from the analysis cannot be entirely foreseen at the time of writing the statistical analysis plan evolving trial conduct may require some further definition of patients to be excluded, at the end of the trial, but prior to unblinding.

Aspects to be considered (but not limited to) when determining the evaluability of data are as follows:

- Inclusion and exclusion criteria
- Acceptable timings for visit dates and measurements
- Compliance with treatment
- Incorrect randomization/treatment
- Concomitant therapies

As far as possible ITT principle will be guaranteed so it is not expected to have protocol deviations excluding patients from the ITT population.

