13.5 Extent of investigational medicinal product exposure and compliance

Average number of doses taken per day will be calculated. Percentage of patients will be obtained for each of the categories defined below:

- <0.9 average doses/day taken
- ≥ 0.9 and <1.1 average doses/day taken
- ≥ 1.1 average doses/day taken

Duration of IMP exposure is defined as last dose date – first dose date, regardless of unplanned intermittent discontinuations. Duration of IMP exposure will be summarized descriptively as a quantitative variable (number, mean, SD, median, minimum, and maximum).

In addition, duration of treatment exposure will also be summarized categorically by numbers and percentages for each of the following categories and cumulatively according to these categories: Up to 1 weeks, >1 to 2 weeks; >2 to 3 weeks; >3 to 4weeks; >4 to 6 weeks; >6 weeks

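### The compliance formula divides by days between visits, so off-drug days before drug return lower the score of a subject who missed no scheduled tablet

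*Protocol*

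**What the plan says.** Protocol 8.6.10 sets the compliance rule: "Non-used drug will be returned to the centre at week 2 and week 6, and compliance will be assessed as" tablets used over "Total number of days between visits", as a percentage. Dosing is daily: "Subjects will be instructed to take 1 tablet orally per day at the same time in the morning, with or without food". It starts the day after Visit 1: "The first dose is to be taken the day after randomisation when study medication has been dispensed to the subject".

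Footnote 12 of the Schedule of Assessments (Protocol 18.15) gives the end of dosing: "Treatment will be taken from Day 1 to Day 42, both inclusive". Protocol 8.4.2 allows Visit 2 on Day 14 ±2 and Visit 3 on Day 42 ±3. At early termination the Visit 3 procedures, including drug return, are done at that visit; no maximum interval from the last dose is given. Protocol 8.6.2 adds: "The wallet cards will contain a surplus of tablets to cover the treatment period and visit windows".

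SAP 13.5 says: "Average number of doses taken per day will be calculated". It reports three bands (below 0.9, 0.9 to below 1.1, and 1.1 or more) and names no denominator. It defines exposure duration as last dose date minus first dose date. SAP 6 lists "Compliance with treatment" among the aspects considered when evaluability is decided before unblinding.

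**The concern.** A compliance percentage should measure the share of scheduled tablets that were taken. With inter-visit days in the denominator, days on which no tablet was due count as missed doses. The figure then mixes two things that a dose-finding trial wants to keep apart: missing tablets while on treatment, and having stopped treatment.

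The figure may be used in two places: the SAP 13.5 bands and the blinded compliance review behind the per-protocol set. The SAP states in its introduction that it does not change the protocol's analysis, and in Section 14 that there are no changes. With no denominator of its own, the protocol formula is therefore the natural default for a programmer, although the SAP does not cite it.

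**Working it through.** The documents state no compliance figure, so there is none to reproduce. The check applies the formula to a subject who takes every scheduled tablet.

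**Inputs.** One tablet per day, first dose on Day 1 (Protocol 8.6.3). Visit 1 is on Day -1 and the first dose is the next day, so there is no Day 0, and Visit 1 to Day 14 is 14 days. The tablet on the visit day is taken before the visit (footnote 9, Protocol 18.15). The visit windows are Days 12–16 and Days 39–45.

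**Formula.** Compliance = 100 × tablets used / days between visits.

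**On schedule.** Visit 1 to Visit 2: 14/14 = 100%. Visit 2 to Visit 3: 28/28 = 100%. Any in-window Visit 3 up to Day 42 also gives 100%.

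**Early stop.** Assume Visit 2 on Day 14 and a last dose on Day 20. Doses on Days 15–20 make 6 tablets in the interval, and 20 in all. The gap to the termination visit is also an assumption, shown as a range:

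| Gap (days) | Interval | Whole period |
|---|---|---|
| 0 | 6/6 = 100% | 20/20 = 100% |
| 1 | 6/7 = 85.7% | 20/21 = 95.2% |
| 3 | 6/9 = 66.7% | 20/23 = 87.0% |
| 7 | 6/13 = 46.2% | 20/27 = 74.1% |

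Later stops are less sensitive. With a last dose on Day 28, the interval figure falls below 90% at a gap of 2 days (14/16 = 87.5%) and the whole-period figure at 4 days (28/32 = 87.5%). With a last dose on Day 35, these happen at 3 days (21/24 = 87.5%) and 4 days (35/39 = 89.7%).

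**Late Visit 3, with dosing ended on Day 42.** Visit 3 on Day 45 gives:
- Visit 2 on Day 12: 30/33 = 90.9%
- Visit 2 on Day 14: 28/31 = 90.3%
- Visit 2 on Day 16: 26/29 = 89.7%
- whole period: 42/45 = 93.3%

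If dosing instead continued to Day 45 from surplus tablets, the Visit 2 on Day 14 case would give 31/31 = 100%.

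**Could the SAP's exposure duration serve as the denominator?** Last minus first dose date is one day short of the number of dosing days, so n consecutive daily doses give n/(n − 1). For 42 doses this is 42/41 = 1.02 and for 20 doses 20/19 = 1.05, both in the middle band. But n/(n − 1) ≥ 1.1 whenever n ≤ 11. An adherent subject who stops after 2 to 11 doses would fall in the top band; 5 doses give 5/4 = 1.25. If that subject returned the drug on Day 14, the protocol formula would give 5/14 = 0.36. True adherence is 1.00.

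**With days of scheduled dosing, inclusive, as denominator,** every case above gives 100% (for example 28/28 and 6/6).

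**The case against.** The case against is substantial, and several parts of it stand.

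- **A reader might infer that adherent subjects are classed as non-compliant.** The documents do not support that. The formula has no cut-off. The protocol's withdrawal category for non-compliance (8.5.2) rests on more than 6 consecutive days without drug, not on this percentage. The SAP bands are descriptive.
- **A reader might infer that stopping early lowers the score.** It does not by itself. The termination visit closes the interval, and a same-day visit gives 100%. Only a gap after the last dose matters, and the documents say nothing about how long gaps will be. The expected withdrawal rate of around 15% covers all causes and does not count delayed visits.
- **The late Visit 3 effect is small and conditional.** It needs dosing to end on Day 42, whereas the surplus supplied for visit windows may suggest that dosing can continue. Only one corner of the windows falls below 0.9, and only per interval.
- **A reader might infer that a tolerability signal in the higher-dose arms would be misread as poor tablet-taking.** Protocol 5.2 does call the common adverse events dose related, so a difference between arms is plausible, but none is shown. Reasons for discontinuation, drug withdrawal due to an adverse event, and exposure duration are all recorded or summarised separately.
- **Exclusion from the per-protocol set is not automatic.** It depends on a documented review before unblinding that has no numeric threshold.

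One argument does not stand: that the SAP's silence leaves nothing wrong. The protocol states a formula, and followed as written it scores an adherent subject below 100%. The only other quantity to hand in SAP 13.5 fails for very early stoppers.

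**Conclusion.** The point holds in a limited form. The denominator in Protocol 8.6.10 counts off-drug days before drug return as missed doses. The loss can be large for an early stopper whose termination visit is delayed (46.2% for the interval and 74.1% overall at an assumed 7-day gap) and is zero with no gap. For completers it is at most about 10 percentage points per interval (89.7% at worst) and under 7 over the whole period (93.3%), and only if dosing ends on Day 42.

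The consequences are confined to the compliance table and, depending on the blinded review, the per-protocol sensitivity set. The primary intent-to-treat analysis is unaffected. The early-stop figures rest on assumed stop and return dates; the late-visit figures rest on footnote 12. The correction is worth making before database lock because a stated formula gives a wrong value and the remedy is only wording.

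**What to change.** In Protocol 8.6.10 and SAP 13.5, define the denominator once as the number of days of scheduled dosing in the interval, first to last inclusive, ending at the permanent stop date for subjects who stop early. State whether the SAP figure is per interval or for the whole treatment period. Use the same definition for the 0.9 and 1.1 bands and for the compliance information given to the blinded per-protocol review. Early stopping can stay in the exposure-duration summary already planned in SAP 13.5.

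The sponsor should also reconcile the surplus-tablet statement in Protocol 8.6.2 with footnote 12 of Protocol 18.15, so that the last scheduled dosing day is unambiguous when Visit 3 falls after Day 42. The proposed denominator works under either reading.

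Cost: a wording change in two documents and a small programming change. First and last dose dates are already needed for SAP 13.5, so no new data are required.
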